## **6.3 Other Variables**

### **6.3.1 Variables Related to Study Drugs**

#### **Treatment Groups**

Table 2 below presents the groups to which subjects are randomized.

**Table 2 Treatment groups**

Randomization Arm Code (ARMCD)	Randomization Arm (ARM)	Treatment Group (Labels in TLFs)	
G600	GABAPENTIN ENACARBIL 600 mg QD	Gabapentin enacarbil	Total
P	PLACEBO	Placebo	

#### **Analysis Date of First Dose**

Dates of first dose of study drug in run-in period, treatment period and follow-up period are collected in the Study Drug Dosing 3 eCRF. Analysis dates of first dose in run-in period, treatment period and follow-up period are defined as Date of First Dose of Study Drug

(RUN-IN PERIOD), Date of First Dose of Study Drug (TREATMENT PERIOD) and Date of First Dose of Study Drug (FOLLOW UP PERIOD), respectively.

### **Analysis Date of Last Dose**

Dates of last dose of study drug in run-in period, treatment period and follow-up period are collected in the Study Drug Dosing 3 eCRF. Analysis dates of last dose in run-in period, treatment period and follow-up period are defined as Date of Last Dose of Study Drug (RUN-IN PERIOD), Date of Last Dose of Study Drug (TREATMENT PERIOD) and Date of Last Dose of Study Drug (FOLLOW UP PERIOD), respectively.

### **Duration of Exposure in Treatment Period**

For each subject, duration of exposure in treatment period will be calculated in days, using the following formula:

(‘Analysis Date of Last Dose in Treatment Period’ - ‘Analysis Date of First Dose in Treatment Period’) + 1

### **Duration of Exposure in Entire Period**

For each subject, duration of exposure in entire period will be calculated in days, using the following formula:

(‘Analysis Date of Last Dose in Follow-up Period’ - ‘Analysis Date of First Dose in Run-in Period’) + 1

If subjects do not take any study drugs in follow-up period, ‘Analysis Date of Last Dose in Follow-up Period’ will be replaced with ‘Analysis Date of Last Dose in Treatment Period’.

### **Compliance in Treatment Period**

For each subject, compliance of study drug in treatment period will be calculated in %, using the following formula:

$$\frac{\text{Total number of study drugs actually taken in treatment period}}{\text{Duration of Exposure in Treatment Period} \times 2} \times 100$$

where

‘Total number of study drugs actually taken in treatment period’ =  
(Sum of “Number Dispensed” for 0WEEK, 1WEEK, 2WEEK, 4WEEK, 6WEEK, 8WEEK and 10WEEK in the Study Drug Accountability 2 eCRF) minus (Sum of “Number Returned” for 0WEEK, 1WEEK, 2WEEK, 4WEEK, 6WEEK, 8WEEK and 10WEEK in the Study Drug Accountability 2 eCRF) minus (Sum of “Number Lost” for 0WEEK, 1WEEK, 2WEEK, 4WEEK, 6WEEK, 8WEEK and 10WEEK in the Study Drug Accountability 2 eCRF)

### **Compliance in Entire Period**

For each subject, compliance of study drug in entire period will be calculated in %, using the following formula:

$$\frac{\text{Total number of study drugs actually taken in entire period}}{\text{Duration of Exposure in Entire Period} \times 2} \times 100$$

where

‘Total number of study drugs actually taken in entire period’ =  
(Sum of “Number Dispensed” for -1WEEK, 0WEEK, 1WEEK, 2WEEK, 4WEEK,  
6WEEK, 8WEEK, 10WEEK and 12WEEK in the Study Drug Accountability 2 eCRF)  
minus (Sum of “Number Returned” for -1WEEK, 0WEEK, 1WEEK, 2WEEK, 4WEEK,  
6WEEK, 8WEEK, 10WEEK and 12WEEK in the Study Drug Accountability 2 eCRF)  
minus (Sum of “Number Lost” for -1WEEK, 0WEEK, 1WEEK, 2WEEK, 4WEEK,  
6WEEK, 8WEEK, 10WEEK and 12WEEK in the Study Drug Accountability 2 eCRF)

### 6.3.2 Demographic Characteristic Variables

#### Duration of Onset of Restless Legs Syndrome

Duration of Onset of Restless Legs Syndrome in years is defined as:

$$(\text{‘Date of Visit of Run-in Period’} - \text{‘Date of Diagnosis’})/365.25$$

where ‘Date of Diagnosis’ is imputed by the following rules;

Reported Date (from the eCRF)	Date of Diagnosis (Derived)
MM/YYYY	01/MM/YYYY
--/YYYY	01/01/YYYY
MM/----, or --/---- (Unknown)	No imputation

### 6.3.3 Previous and Concomitant Medication

Previous medication is defined as medication with at least one dose taken before ‘Date of Visit of Run-in Period’ (exclusive).

Concomitant medication is defined as medication with at least one dose taken between ‘Date of Visit of Run-in Period’ (inclusive) and ‘Date of Last Study Evaluation’ (inclusive).

## 7 STATISTICAL METHODOLOGY

### 7.1 General Considerations

- For continuous variables, descriptive statistics will include the number of subjects (n), mean, standard deviation, median, minimum and maximum.
- The number of digits to be used for the mean, standard deviation and median will be added one more digit to raw data with rounding off. The minimum and maximum will be presented with the same number of digit(s) as raw data.
- Frequencies and percentages will be displayed for categorical data. Percentages by categories will be based on the number of subjects with no missing data, i.e. will add up to 100%.
- Frequencies and percentages will be rounded to one decimal place.

- For time-to-event variables, the number and percentage of subjects with the event using Kaplan-Meier method, the cumulative event rate will be estimated and a plot will be constructed.
- All data processing, summarization, and analyses will be performed using SAS Drug Development version 4.5 and SAS version 9.4. Specifications for tables, figures, and data listing formats can be found in the TLF specifications for this study.
- For continuous variables that are recorded as “< X” or “> X”, the value of “X” will be used in the calculation of summary statistics. The original values will be used for the listings.
- MedDRA/J (version 19.0) will be used as the coding dictionary for adverse event and medical history.
- WHODDE (J-Drug(2016H1)) will be used as the coding dictionary for previous and concomitant medication.
- All statistical results will be presented, as appropriate, by treatment group, and by scheduled visit; the schedule of assessments is provided in section [7.10](#)
- For the definition of subgroups of interest please refer to section [7.8](#)

## 7.2 Study Population

### 7.2.1 Disposition of Subjects

The following subject data will be summarized and presented:

[Analysis population: All subjects with informed consent, Analysis group: Total]

- Number of subjects with informed consent, discontinued before run-in period, administered at least one dose of study drug in run-in period, discontinued in run-in period, randomized, and
- Number and percentage of subjects discontinued before run-in period, by primary reason for study discontinuation.

[Analysis population: All subjects with administered at least one dose of study drug in run-in period, Analysis group: Total]

- Number and percentage of subjects discontinued in run-in period, by primary reason for study discontinuation.

[Analysis population: All randomized subjects, Analysis group: Placebo, Gabapentin enacarbil, Total]

- Number and percentage of subjects randomized in each analysis set, administered at least one dose of study drug in treatment period,
- Number and percentage of subjects completed and discontinued the treatment period, by primary reason for study discontinuation, and
- Number and percentage of subjects excluded from FAS, PPS and SAF by reason for exclusion defined in section [5.1](#) [5.2](#) and [5.3](#)

Following data will be presented graphically by treatment group for the all randomized subjects. Subjects who complete the study will be censored at the date of last evaluation.

- Time to study discontinuation using a Kaplan-Meier plot.

[Analysis population: All subjects with administered at least one dose of study drug in follow up period, Analysis group: Placebo, Gabapentin enacarbil, Total]

- Number and percentage of subjects completed and discontinued the follow up period, by primary reason for study discontinuation.

### **7.2.2 Demographic and Other Baseline Characteristics**

Demographic and other baseline characteristics will be summarized by descriptive statistics and frequency tabulations (Table 3), by treatment group for the SAF, FAS and PPS.

Baseline values of efficacy variables will be summarized by descriptive statistics and frequency tabulations (Table 4), by treatment group for the FAS and PPS.

Medical history is coded in MedDRA, and will be summarized by System Organ Class (SOC) and Preferred Term (PT), by treatment group for the SAF.

**Table 3 Demographic and baseline characteristics**

Item	Classification
Sex	1: Male 2: Female
Age (Years) [Informed Consent]	Measurement value 1: < 65 2: >= 65
Height (cm) [Run-in Period]	Measurement value
Weight (kg) [Run-in Period]	Measurement value 1: < 60 2: >= 60
BMI (kg/m  ) [Run-in Period]	Measurement value 1: < 25 2: >= 25
Duration of Onset of Restless Legs Syndrome (Years)	Measurement value 1: < 1 2: >= 1 to < 5 3: >= 5 to < 10 4: >= 10 5: Unknown
Family History of RLS	1: No 2: Yes
Age (Years) [Run-in Period]	Measurement value 1: < 50 2: >= 50
Estimated creatinine clearance (mL/min) [Run-in Period]	Measurement value 1: >= 60 to < 90 2: >= 90

**Table 4 Baseline values of efficacy variables**

Item	Classification
IRLS score	Measurement value 1: <= 20 2: > 20 to <= 30 3: > 30 to <= 40
PSQI Sleep Quality	Measurement value
PSQI Sleep Latency	Measurement value
PSQI Sleep Duration	Measurement value
PSQI Habitual Sleep Efficiency	Measurement value
PSQI Sleep Disturbance	Measurement value
PSQI Use of Sleeping Medication	Measurement value
PSQI Daytime Dysfunction	Measurement value
PSQI Global Score	Measurement value
Total Score of Athens Insomnia Scale	Measurement value
RLS pain score	Measurement value
EQ-5D-5L VAS Score	Measurement value
EQ-5D-5L Mobility	1: I have no problems in walking about 2: I have slight problems in walking about 3: I have moderate problems in walking about 4: I have severe problems in walking about 5: I am unable to walk about
EQ-5D-5L Self-Care	1: I have no problems washing or dressing myself 2: I have slight problems washing or dressing myself 3: I have moderate problems washing or dressing myself 4: I have severe problems washing or dressing myself 5: I am unable to wash or dress myself
EQ-5D-5L Usual Activities	1: I have no problems doing my usual activities 2: I have slight problems doing my usual activities 3: I have moderate problems doing my usual activities 4: I have severe problems doing my usual activities 5: I am unable to do my usual activities
EQ-5D-5L Pain/Discomfort	1: I have no pain or discomfort 2: I have slight pain or discomfort 3: I have moderate pain or discomfort 4: I have severe pain or discomfort 5: I have extreme pain or discomfort
EQ-5D-5L Anxiety/Depression	1: I am not anxious or depressed 2: I am slightly anxious or depressed 3: I am moderately anxious or depressed 4: I am severely anxious or depressed 5: I am extremely anxious or depressed

### 7.2.3 Previous and Concomitant Medications

Previous and concomitant medications are coded with WHODDE, and will be summarized by preferred WHO name, by treatment group for the SAF.

The following specific medications uses will be summarized by frequency tabulations, by treatment group for the SAF, FAS and PPS.

Prior Dopamine agonists Use	No, Yes
-----------------------------	---------

## **7.3 Study Drugs**

### **7.3.1 Exposure**

Durations of exposure in treatment and entire period will be summarized by descriptive statistics and frequency tabulations, by treatment group for the SAF. The following categories of the durations of exposure (days) will be defined:

- < 29 (4 weeks)
- >= 29 (4 weeks) to < 57 (8 weeks)
- >= 57 (8 weeks) to < 85 (12 weeks)
- >= 85 (12 weeks)

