\* Follow-up observation will occur on the day of "last dosing of the study drug for the treatment period +8 days," which will be Day 92 in subjects who take the study drug for the treatment period up to Day 84 per protocol.

\* For the subjects discontinued during the run-in period, the compliance status and any AEs will be investigated.

For the subjects discontinued during the treatment period, the tests/observations required at discontinuation will be performed, and then post-treatment follow-up (i.e., the Week 13 procedure) will be performed as far as possible, but this does not require the use of placebo during the follow-up period.

For the subjects discontinued during the follow-up period, the Week 13 procedure will be performed as the tests/observations at discontinuation.

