### **6.2.1 Adverse Events**

TEAE is defined as an adverse event observed after starting administration of the study drug in the treatment period. If the adverse event occurs on the date of first dose of study drug (treatment period) and the onset check box is marked “ONSET BETWEEN FIRST DOSE OF STUDY DRUG IN TREATMENT PERIOD AND FIRST DOSE OF STUDY DRUG IN FOLLOW UP PERIOD”, then the adverse event will be considered treatment-emergent.

A drug-related TEAE is defined as any TEAE with at least possible relationship to study treatment as assessed by the investigator or with missing assessment of the causal relationship.

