#### **7.10.3.1 IRLS score and RLS Pain score**

For the IRLS score and the RLS Pain score, the allowed time windows for analyses are shown in the table below. For data in the treatment period, the data obtained up to 7 days after the day of last dosing in the treatment period will be used.

Analysis visit	Allowable time window	Reference day
Run-in	Day -10 to Day -7	Day 1
Week 0	Day 1	Day 1
Week 1	Day 5 to Day 11	Day 8
Week 2	Day 12 to Day 18	Day 15
Week 4	Day 26 to Day 32	Day 29
Week 6	Day 40 to Day 46	Day 43
Week 8	Day 54 to Day 60	Day 57
Week 10	Day 68 to Day 74	Day 71
Week 12	Day 82 to Day 88	Day 85
End of treatment	Day 2 to Reference day +7 days	Day of last dosing in the treatment period
Follow-up	Reference day +5 days to Reference day +11 days	Day of last dosing in the treatment period

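### Minor, descriptive safety tables only: courses of exactly 28, 56 or 84 days fall one exposure category too low, and the drug-related definition, read literally, omits events recorded as Not assessable

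*SAP*

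**What the plan says.** **Exposure.** SAP 6.3.1 states that "duration of exposure in treatment period will be calculated in days, using the following formula": last dose date minus first dose date, plus 1. The entire-period duration has the same form, from the first run-in dose to the last follow-up dose, with a substitution that begins "If subjects do not take any study drugs in follow-up period" and uses the last treatment-period dose instead. SAP 7.3.1 then says "Durations of exposure in treatment and entire period will be summarized by descriptive statistics and frequency tabulations", with one set of categories for both tables: under 29 days, 29 to under 57, the category ">= 57 (8 weeks) to < 85 (12 weeks", and 85 days or more, labelled 12 weeks. Footnote 4 to the SAP Schedule of Assessments fixes the per-protocol timeline. It places the follow-up visit eight days after the last treatment-period dose, "which will be Day 92 in subjects who take the study drug for the treatment period up to Day 84 per protocol".

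**Drug-related events.** SAP 6.2.1 defines a drug-related TEAE as "any TEAE with at least possible relationship to study treatment as assessed by the investigator or with missing assessment of the causal relationship". Protocol 5.5.3 has four causality categories: Not related, Possible, Probable and Not assessable. It places the last three together as events whose relationship to study drug is not ruled out. Not assessable has its own definition there: a report that cannot be judged because the information is inadequate or conflicting. It is an answer that the investigator records, not an empty field.

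**The concern.** The evaluation of safety at 600 mg is a stated objective (Protocol 2.1, SAP 3.1), and these are its exposure and causality tables. A subject who takes study drug for exactly the planned 12 weeks would be listed as having had 8 to under 12 weeks of exposure. The table would then understate how many subjects received the full course.

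The causality definition has a similar flaw. A blank assessment counts as drug-related, but a recorded judgement that causality cannot be assessed does not, if the words are followed as written. The drug-related tables would then be narrower than the protocol's own class of events not ruled out.

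**Working it through.** **1. Exposure categories**

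Inputs: the Day 84 last dose and Day 92 follow-up (SAP Schedule of Assessments, footnote 4), the exposure formula (SAP 6.3.1), the categories (SAP 7.3.1), and Day 1 as the day of formal registration (SAP 7.10.3). I assume that the first treatment-period dose is taken on Day 1.

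The plan's own timeline reproduces: 84 + 8 = Day 92.

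Exposure = last − first + 1:

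| Course | Days | Category as written | Category with cut points 28/56/84 |
|---|---|---|---|
| Day 1 to 28 (4 weeks) | 28 − 1 + 1 = 28 | < 29 | 28 to < 56 |
| Day 1 to 56 (8 weeks) | 56 − 1 + 1 = 56 | 29 to < 57 | 56 to < 84 |
| Day 1 to 84 (12 weeks) | 84 − 1 + 1 = 84 | 57 to < 85 | ≥ 84 |

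The edges 29, 57 and 85 are the scheduled days of the Week 4, 8 and 12 visits. A visit-day number is one more than the number of days dosed before that visit, and this is the source of the one-day offset.

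The Week 12 window is "Day 82 to Day 88" with reference Day 85. If the last dose is taken on the evening before the visit (an assumption):

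- visits on Days 82 to 84 give 81 to 83 days, below the top category under either set of cut points;
- a visit on the target Day 85 gives 84 days, below the top category as written and in it with the cut point at 84;
- visits on Days 86 to 88 give 85 to 87 days, in the top category either way.

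Under that assumption, only subjects seen after the target day reach the category labelled 12 weeks.

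Entire-period table: a full course is 7 + 84 + 7 = 98 days, in the top category either way. Only totals of exactly 28, 56 or 84 days are affected. With a 7-day run-in and no follow-up placebo, these belong to subjects who stop after 28 − 7 = 21, 56 − 7 = 49 or 84 − 7 = 77 treatment days.

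**2. Drug-related definition**

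| Investigator's record | Protocol 5.5.3: not ruled out? | SAP 6.2.1, read literally: drug-related? |
|---|---|---|
| Not related | No | No |
| Possible | Yes | Yes |
| Probable | Yes | Yes |
| Not assessable | Yes | Not named: neither missing nor plainly at least possible |
| Blank | Not addressed | Yes |

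The definition feeds 6 of the 13 rows of the SAP 7.5.1 overview table, 4 of its 9 SOC/PT summaries, and the table of drug-related TEAEs by severity. The documents give no count of Not assessable events.

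**The case against.** **The edges are a convention.** SAP 7.5.1 uses 29, 57 and 85 with the same week labels for TEAE onset intervals, so a change to SAP 7.3.1 alone might seem to create a mismatch. It does not. The onset intervals count days from first dosing and label Day 1 as 0 weeks, so Day 29 is correctly 4 weeks on that scale. The exposure variable is a duration that counts both end days, and on that scale 4 weeks is 28. A footnote can state the difference.

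**The harm is limited.** This stands. Each category prints its day limits, and mean and median exposure are reported and are unaffected. Completion has its own table in SAP 7.2.1: "Number and percentage of subjects completed and discontinued the treatment period, by primary reason for study discontinuation".

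**The causality gap may not be real in practice.** This stands in part. The SAP presents itself as an elaboration of the protocol, so the protocol's class is probably intended. Protocol 7.5.1 speaks of related events and does not tie that phrase to the class in Protocol 5.5.3. Programming may already treat Not assessable as related or as missing, but SAP 6.2.1 does not say so. In the by-relationship tables of SAP 7.5.1, the event counts would still show the category. The subject counts take the highest degree of relationship, and the SAP does not say where Not assessable ranks.

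**Stronger readings to avoid.** A reader might infer that every completer is misclassified, or that the effect is confined to completers. The documents support neither. Some completers will have fewer or more than 84 days, and discontinued subjects with exactly 28 or 56 days are moved too. Nor do the documents show that Not assessable events will in fact be dropped; that follows only from a literal reading.

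**Conclusion.** Both points hold as minor faults in descriptive safety tables. The categories do not enter the primary model, the PPS rules (2 weeks of dosing, at least 70% compliance) or the compliance formula, which uses the duration in days.

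1. Exposure categories, high confidence. A course of exactly 28, 56 or 84 days falls one category too low. The subjects moved are those with exactly these durations, whether they completed or discontinued. Their number depends on actual dosing dates and cannot be computed from the documents. For the Day 84 course, the result rests on a first dose on Day 1.

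2. Drug-related definition, moderate confidence. Read literally, SAP 6.2.1 is narrower than Protocol 5.5.3 by the category Not assessable. The number of events concerned cannot be computed, so nothing can be said about how far the drug-related counts would change.

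**What to change.** - **SAP 7.3.1:** use < 28, 28 to < 56, 56 to < 84 and ≥ 84 days, for both the treatment-period and the entire-period table. This does not turn the top category into a completer category, because subjects with 81 to 83 days stay below it. Completion should be read from SAP 7.2.1.
- **SAP 7.5.1:** leave the onset intervals as they are and add a footnote that they are study-day numbers, with Day 1 as 0 weeks.
- **SAP 6.2.1:** define a drug-related TEAE as one assessed as Possible, Probable or Not assessable, or with the assessment missing, in line with Protocol 5.5.3.

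The cost is SAP wording and table programming, done before unblinding. Drug-related counts may rise, by an amount that the documents do not allow to be computed.

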### **7.3.2 Study drug Compliance**

Study drug compliances in treatment and entire period will be summarized by descriptive statistics and frequency tabulations, by treatment group for the SAF. The following categories of the study drug compliances (%) will be defined:

- < 50
- >= 50 to < 75
- >= 75 to < 90
- >= 90
- Unknown

## **7.4 Analysis of Efficacy**

### **7.4.1 Analysis of Primary Endpoint**

#### **7.4.1.1 Primary Analysis**

The primary analysis will be performed using the FAS.

The primary efficacy endpoint is the change from baseline in IRLS score at the end of treatment period. Using a repeated measures analysis of variance model, so-called Mixed Model of Repeated Measurements (MMRM) model, having the following average structure, the adjusted mean in each treatment group and its difference (gabapentin enacarbil group - placebo group) at the end of treatment period (Week 12) will be calculated, with comparison between the placebo group and the gabapentin enacarbil group:

Change in IRLS score at each time point

$$= \text{Baseline IRLS score} + \text{Age category}^{\ast 1} + \text{Estimated creatinine clearance category}^{\ast 2} + \\ \text{Treatment group} + \text{Time point} + \text{Treatment group} \times \text{Time point}$$

$\ast^1$  Age category: < 50 years and  $\geq$  50 years

$\ast^2$  Estimated creatinine clearance category:  $\geq$  60 to < 90 mL/min and  $\geq$  90 mL/min

Compound symmetry will be used as the covariance structure for repeated measures of the response variable. A two-sided significance level of 0.05 will be used for statistical tests.

The least-squares mean estimates of the change from baseline in IRLS score at Week 12, the estimates of treatment effect (e.g., least-squares mean change from baseline in IRLS score for gabapentin enacarbil group minus the least-squares mean change from baseline in IRLS score for placebo group) and the corresponding 95% CIs will be reported.

